## **2.7.2 Deaths**

Separate summary and listing will be provided for deaths. The number of deaths resulting from SAEs suspected to be related to study treatment and SAEs irrespective of study treatment relationship will be provided by SOC and PT.

## **2.7.3 Laboratory data**

The summary of laboratory evaluations will be presented for two groups of laboratory tests (hematology and serum chemistry). Descriptive summary statistics for the change from baseline to each study visit will be presented. These descriptive summaries will be presented by cohort, test group, laboratory test and treatment group. Change from baseline will only be summarized for subjects with both baseline and post baseline values. In addition, Summary of notable abnormalities of key laboratory tests will be provided by treatment group. Detail on notable abnormalities derivations will be specified in [Section 5.3](#).

## **2.7.4 Other safety data**

### **2.7.4.1 Vital signs**

Analysis of the vital sign measurements using summary statistics for the change from baseline for each post-baseline visit will be performed. These descriptive summaries will be presented by cohort, vital sign and treatment group. Change from baseline will only be summarized for subjects with both baseline and post-baseline values.

The number and percentage of subjects with newly occurring notable vital signs will be presented. Criteria for notable vital sign abnormalities are provided in [Table 2-7](#) below. A listing of subjects with newly occurring notably abnormal vital signs will be provided.

**Table 2-7 Criteria for notable vital sign abnormalities**

[figure not shown]
Vital sign (unit)	Notable abnormalities
Systolic blood pressure (mmHg)	$\geq 140$ mmHg or $< 90$ mmHg
Diastolic blood pressure (mmHg)	$\geq 90$ mmHg or $< 60$ mmHg
Pulse (bpm)	$> 100$ bpm or $< 60$ bpm

[figure not shown]
## **2.9 PD and [REDACTED]/PD analyses**

[figure not shown]
The [REDACTED] other clinically important endpoints, such as PSAD, REU, LPPAI will be investigated if appropriate.

[figure not shown]
## **2.11 Patient-reported outcomes**

[figure not shown]
Please refer to [Section 2.6](#) and [Section 2.13](#) for the analysis method of Patient-reported outcomes.

## **2.14 Interim analysis**

Primary endpoint analysis will be performed after all subjects have completed Week 16 visit. Additional analyses may be performed to support health authority interactions as necessary. At the End of Study, a final analysis will be performed when all subjects have completed the

last study visit.

[figure not shown]
### 3 Sample size calculation

Total sample size planned for this study is 108 with 36 subjects in each subtype.

For each subtype, 24 secukinumab 300 mg Q4W treatment regimen subjects and 12 placebo subjects assures the 71% probability to claim positive PoC results, based on the assumptions that the placebo IGA responder rate is 20% and secukinumab 300 mg Q4W placebo difference (delta) of the IGA responder rates is at least 30%.

For different response rate assumptions on the secukinumab 300 mg Q4W and placebo dose regimens, [Figure 3-1](#) and [Table 3-1](#) reported below show that there is no substantial difference in the probability of claiming a successful PoC results between randomization ratios 1:1 and 2:1. Considering the absence of previous lichen planus secukinumab data, randomization 2:1 is chosen for this study, to assure the collection of more efficacy and safety data on lichen planus secukinumab subjects, while limiting the number of subjects exposed to placebo. [Figure 3-1](#) and [Table 3-1](#) also show that the probability of claiming positive PoC results being around 70% when the secukinumab 300 mg Q4W and placebo difference (delta) of the IGA responder rates is 30% in any scenario, and greater than 85% when the secukinumab 300 mg Q4W and placebo difference (delta) of the IGA responder rates is 40% in any scenario.

[figure not shown]
**Figure 3-1 Operating Characteristics on different randomization ratio and different response rate assumption**

[figure not shown]

**Table 3-1      Operating Characteristics on different randomization ratio and different response rate assumption**

Secukinumab response rate	Placebo response rate	Probability to meet target efficacy with AIN 18: PBO 18	Probability to meet target efficacy with AIN 24: PBO 12
A(small)=0.4	0.1	0.838	0.793
B(moderate)=0.5	0.1	0.945	0.923
C(high)=0.6	0.1	0.987	0.978
D(very high)=0.7	0.1	0.998	0.996
E(extreme high)=0.8	0.1	1.000	1.000
A(small)=0.4	0.2	0.543	0.503
B(moderate)=0.5	0.2	0.767	0.712
C(high)=0.6	0.2	0.915	0.871
D(very high)=0.7	0.2	0.980	0.960
E(extreme high)=0.8	0.2	0.998	0.993
A(small)=0.4	0.3	0.282	0.255
B(moderate)=0.5	0.3	0.520	0.454
C(high)=0.6	0.3	0.751	0.675
D(very high)=0.7	0.3	0.908	0.856
E(extreme high)=0.8	0.3	0.980	0.961

\*Calculation for Operating Characteristics was based on QTD version 3.0.0

## 5 Appendix

### 5.1 Imputation rules

#### 5.1.1 Study drug

Any partial dates will be imputed as follows:

The earlier day will be taken from below

- The last day in the month and
- The end day of the corresponding Treatment Period

#### 5.1.2 AE date imputation

Impute AE end date:

1. If the AE end date 'month' is missing, the imputed end date should be set to the earliest of the (min (last visit date, last dose date + 84 days), 31DECYYYY, date of death).
2. If the AE end date 'day' is missing, the imputed end date should be set to the earliest of the (min (last visit date, last dose date + 84 days), last day of the month, date of death).
3. If AE 'year' is missing or AE is ongoing, the end date will not be imputed.

Impute AE start date:

Before imputing AE start date, find the AE start reference date.

1. If the (imputed) AE end date is complete and the (imputed) AE end date < treatment start date then AE start reference date = min(informed consent date, earliest visit date).
2. Else AE start reference date = treatment start date
  1. If the AE start date 'year' value is missing, the date uncertainty is too high to impute a rational date. Therefore, if the AE year value is missing, the imputed AE start date is set to NULL.
  2. If the AE start date 'year' value is less than the treatment start date year value, the AE started before treatment. Therefore:
    - a. If AE 'month' is missing, the imputed AE start date is set to the mid-year point (01JULYYYY).
    - b. Else if AE 'month' is not missing, the imputed AE start date is set to the mid-month point (15MONYYYY).
  3. If the AE start date year value is greater than the treatment start date year value, the AE started after treatment. Therefore:
    - a. If the AE month is missing, the imputed AE start date is set to the year start point (01JANYYYY).
    - b. Else if the AE month is not missing, the imputed AE start date is set to the later of

(month start point (01MONYYYY), AE start reference date + 1 day).

4. If the AE start date year value is equal to the treatment start date year value:
  - a. And the AE month is missing the imputed AE start date is set to the AE reference start date + 1 day.
  - b. Else if the AE month is less than the treatment start month, the imputed AE start date is set to the mid-month point (15MONYYYY).
  - c. Else if the AE month is equal to the treatment start date month or greater than the treatment start date month, the imputed AE start date is set to the later of (month start point (01MONYYYY), AE start reference date + 1 day).

If complete (imputed) AE end date is available and the imputed AE start date is greater than the (imputed) AE end date, then imputed AE start date should be set to the (imputed) AE end date.

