- Subjects, whether they are willing to continue attending further study visits or not, should attend an End of Treatment (EOT) visit of the study period during which they discontinued (EOT 1 for discontinuation during Treatment Period 1 and EOT 2 for discontinuation during Treatment Period 2). The scheduled visit that was planned to take place will then not be performed and will be replaced by the EOT visit.
- Subjects who are willing to continue will attend visits until Week 16 or Week 32 according to the schedule and will then move to the Follow-up period.
- Subjects who are unwilling to continue attending study visits will move directly to the Follow up period after their EOT visit
- Subjects who discontinue study at the same time as study treatment will end their participation after their EOT visit (see also [Section 9.1.2](#)).

The investigator must also contact the IRT to register the subject's discontinuation from study treatment.

If discontinuation occurs because treatment code has been broken, please refer to [section 6.6.3](#).

If the subject fails to return for EOT assessments for unknown reasons, every effort (e.g. telephone, e-mail, letter) should be made to contact the subject/pre-designated contact as specified in the Lost to Follow-up section. This contact should preferably be done according to the study visit schedule.

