**Adverse events**

Treatment emergent AEs (events started after the first dose of study treatment and within 84 days after week 32, or events present prior to the first dose of study treatment but increased in severity based on preferred term within 84 days after week 32) will be summarized. Only primary paths within MedDRA will be considered for AE reporting.

AEs will be summarized by presenting, for each treatment group, the number and percentage of subjects having any AE, having an AE in each primary system organ class and having each individual AE (preferred term). Summaries will also be presented for AEs by severity and for study treatment related AEs. If a subject reported more than one AE with the same preferred term, the AE with the greatest severity will be presented. If a subject reported more than one AE within the same primary system organ class, the subject will be counted only once with the greatest severity at the system organ class level, where applicable.

[figure not shown]
Separate summaries will be provided for death, SAE, other significant AEs leading to discontinuation and AEs leading to study treatment discontinuation.

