## 2.7 Analyses of safety endpoints

All safety analyses will be based on the safety set. Only those visits that were pre-planned in the protocol will be reported in tables for safety variables.

Analysis of adverse events will be based on treatment emergent events, which are defined as events started on or after the first dose of study treatment or events present prior to the first dose of study treatment but increased in severity based on preferred term and on or before last dose + 84 days.

Other safety variables including LAB, Vitals will be evaluated based on on-treatment events, which are defined as any events that happened after first dose of study treatment and on or before last dose +84 days.

Safety analysis will be performed on actual treatment, for patients in any of the three cohorts and in each of the three cohorts, respectively. Analyses will be presented by Treatment Period 1 and entire treatment period and by treatment groups as specified in [Table 2-1](#).

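### When both AE dates are partial, SAP 5.1.2 can move an event recorded wholly after last dose + 84 days back inside the treatment-emergent window

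*SAP*

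**What the plan says.** SAP 5.1.2 imputes the AE end date first. With the day missing, the end is "set to the earliest of the (min (last visit date, last dose date + 84 days), last day of the month, date of death". With the month missing, it is the earliest of "min (last visit date, last dose date + 84 days), 31DECYYYY, date of death". The only exemption is: "If AE 'year' is missing or AE is ongoing, the end date will not be imputed". Neither rule has a lower limit at the recorded month or year.

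A start date with only the day missing, in or after the month of first dose, goes to the later of the first of the recorded month and the day after a reference date, normally the first dose. The section closes with a consistency rule, for records where the end is known or imputed in full. It resets the start to the end whenever the start comes out later: "then imputed AE start date should be set to the (imputed) AE end date".

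SAP 2.7 sets the upper limit of the treatment-emergent window, in the clause on events that "increased in severity based on preferred term and on or before last dose + 84 days". Protocol 12.5.2 defines the window differently, as "events started after the first dose of study treatment and within 84 days after week 32".

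Protocol 9.1.1 provides for subjects who stop treatment but agree to stay under observation: they "will attend visits until Week 16 or Week 32 according to the schedule and will then move to the Follow-up period".

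SAP 5.1.3, for concomitant medications, includes a guard: an imputed end that precedes the start is replaced by the start. The AE section has no such guard.

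**The concern.** The cap at last visit or last dose + 84 days is sensible for an event that may have run past the window. It is wrong for an event whose recorded month begins after the cap, because the imputed end then contradicts a part of the date that is known. The closing rule treats that end as reliable and moves a partial start back to it. The event lands on the cap, and because the window limit is inclusive it is counted.

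This matters for the AE and SAE tables and for the exposure-adjusted rates in SAP Table 2-6. SAP 2.4.1 stops exposure no later than last dose + 84 days, so a relocated event enters the numerator while its actual time lies outside the denominator. With 24 active and 12 placebo subjects per cohort, and a display threshold of two cases per group for common AEs, one relocated event can be visible.

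**Working it through.** The documents state no figure on this point, so the check applies the rules literally to example dates.

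**Example A: both dates partial, stop in Treatment Period 1**
- First dose is 1 Feb 2021 (Day 1). Last dose is at Week 4 (Day 29, 1 Mar 2021).
- Window end = 1 Mar + 84 days = 24 May 2021 (Day 113).
- The subject attends to Week 16 and then completes the 8-week follow-up, so the last visit is Week 24 (Day 169, 19 Jul 2021).
- The AE is recorded as June 2021 to June 2021, both days missing (possible Days 121 to 150).
- End: min(19 Jul, 24 May) = 24 May; min(24 May, 30 Jun) = 24 May.
- Start: max(1 Jun, 2 Feb) = 1 Jun, which is later than 24 May, so it is reset to 24 May.
- Result: the start falls on last dose + 84 days and counts as treatment-emergent. The earliest start compatible with the record is 1 Jun (8 days past the window) and the latest is 30 Jun (37 days past).

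**Example B: both dates partial, stop in Treatment Period 2**
- Day 1 is 4 Jan 2021, the last dose is at Week 16 (Day 113), the window ends on Day 197 (19 Jul 2021), and the last visit is Day 281.
- An AE recorded as September 2021 to September 2021 gets 19 Jul for both dates. Before the reset its start was 1 Sep (Day 241), outside the window.
- With this dosing pattern and each of 365 consecutive calendar dates as Day 1, such an AE in the first full month after the window was relocated in 365 of 365 cases. With a floor at the recorded month it was 0 of 365. This tests the logic of the rule, not how often it will bite.

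**Example C: complete start, partial end.** With the subject of Example A, take a start of 10 Jun 2021 and an end of June 2021. The end is imputed to 24 May, 17 days before the start. The duration formula in SAP 2.1.1.1 then gives -17 + 1 = -16 days. The start is untouched, so treatment-emergent status does not change.

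**Records not reclassified:** a complete start, a complete end, an ongoing AE, or a missing end year.

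**How long can a subject be observed past the window?** Days past = last scheduled visit day - (last dose day + 84), with the last visit on Day 169 for stops in Period 1 and Day 281 for stops in Period 2.
- Day 1: 169 - 85 = 84. Week 16: 281 - 197 = 84.
- Week 4: 169 - 113 = 56. Week 20: 281 - 225 = 56.
- Week 8: 169 - 141 = 28. Week 24: 281 - 253 = 28.
- Week 12: 169 - 169 = 0. Week 28: 281 - 281 = 0.
- Completer: last dose Day 211, window end Day 295, last visit Day 281, so 0.

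**The case against.** **The protocol would count these events anyway.** Its window runs to 84 days after Week 32, that is Day 225 + 84 = Day 309. Example A (Days 121 to 150) is inside it, as is every early-stopper case, since scheduled observation ends by Day 281. This stands: the misclassification is relative to the SAP's definition. It does not rescue the imputation, which gives dates outside the recorded month under either definition. It does show that the two windows need reconciling.

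**SAP 2.7 is ambiguous.** The 84-day limit can be read as attaching only to worsening of pre-existing events, leaving new events with no upper limit. That reading is possible. The less natural one, though: the same section applies the limit to laboratory and vital-sign data, and SAP 2.4.1 stops exposure there.

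**Attendance after stopping is voluntary.** This also stands. An unwilling subject goes from the EOT visit to follow-up: 4 + 8 weeks = 84 days after last dose in Period 1, and 2 + 8 weeks = 70 days in Period 2. Neither extends past the window.

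**The error is small and one-directional.** It adds events to safety tables, hides none, and leaves the primary endpoint untouched. Agreed.

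A reader might infer three stronger points that the documents do not support.
- That any partial end date causes reclassification. The reset acts only on an imputed start, so both dates must be partial.
- That one arm is disadvantaged. Nothing in the documents says which arm will have more early stoppers.
- That completers' late SAEs are pulled in as well. Completers have no scheduled visit past the window, and Protocol 10.1.3 gives two collection limits that disagree: 30 days after Week 40, and 10 weeks after treatment stops. The documents do not settle whether such records would be collected.

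**Conclusion.** The rule is wrong as written, in a narrow set of records. When both AE dates are partial and the recorded month or year begins after the cap, SAP 5.1.2 overrides known date parts and places the event inside the SAP 2.7 window. When only the end is partial, the AE can end before it starts, without a change in classification.

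The records at risk are mainly AEs in subjects who stop treatment early and stay under observation, for up to 84, 56 or 28 days past the window at the last-dose visits listed above. This assumes that the 84-day limit in SAP 2.7 applies to new events, and that a subject who stops in Period 1 completes 8 weeks of follow-up after Week 16. If the protocol's window were adopted, the reclassification of early stoppers' events would disappear and only the wrong dates would remain.

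The expected count among 108 subjects is small and cannot be estimated, because no rate of partial dates is given. This is a minor correction, worth making because the error is systematic and cheap to remove.

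**What to change.** In SAP 5.1.2:

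1. State that an imputed AE end date may not be earlier than the first day of the recorded end month (or end year, if the month is missing), nor earlier than a fully recorded start date. SAP 5.1.3 already has the second guard for concomitant medications.
2. Where the cap would breach this floor, use the end of the recorded month (or year) or the date of death, whichever is earlier.
3. Apply the reset of start to end only after the floor.

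The floor should rest on recorded date parts, not on an imputed start. The start reference date is itself derived from the imputed end, so using the imputed start would be circular. For the same reason, add the first day of a recorded start month to the floor. Otherwise one pattern survives. In Example A, a start of June 2021 with an end recorded only as 2021 gives min(24 May, 31 Dec) = 24 May. That does not breach the year floor of 1 Jan, yet the start is still pulled from 1 Jun to 24 May.

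With the floor, Example B becomes 1 Sep to 30 Sep 2021 and is not treatment-emergent under SAP 2.7.

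Separately, reconcile the treatment-emergent window in SAP 2.7 with Protocol 12.5.2, and say explicitly whether its upper limit applies to new as well as worsening events.

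Cost: a few sentences in the SAP and a short change to the derivation code, with attention to the order of steps. No new data are needed.

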### **Treatment Period 2:**

Treatment Period 2 starts at the Week 16 visit and covers the time until the Week 32 visit.

Depending on the treatment arm, subjects receive the following treatments:

- **Secukinumab 300 mg Q4W arm:** subjects receive continued treatment with secukinumab 300 mg every 4 weeks plus matching placebo injections to maintain treatment blinding.
- **Placebo for 16 weeks followed by secukinumab 300 mg Q2W arm:** subjects are switched to active treatment with secukinumab 300 mg **every 2 weeks** including a weekly induction starting from Week 16 to Week 20, with the exception of subjects achieving remission by Week 16.

The Week 16 injection is the first injection of Treatment Period 2.

Treatment remains blinded during Treatment Period 2. This means that starting at the Week 16 visit all subjects receive an induction consisting of weekly blinded study drug injections (either secukinumab 300 mg or placebo) at Weeks 16, 17, 18, 19 and 20, followed by blinded study drug injections every 2 weeks.

**The last study drug injection is administered at Week 30.** The end of Treatment Period 2 is Week 32. After Week 32, all subjects enter the Follow-up Period.

Subjects who discontinue study treatment prematurely for any reason other than withdrawal of informed consent should **not** be considered as discontinued from the study. Subjects should continue attending planned site visits and perform study assessments until the last visit of the treatment period during which they discontinue (Week 16 or Week 32).

[figure not shown]
Subjects, whether they are willing to continue attending further study visits or not, should attend the End of Treatment visit (EOT) during which they discontinued (EOT 1 for discontinuation

during Treatment Period 1 and EOT 2 for discontinuation during Treatment Period 2). EOT 1 should be performed 4 weeks after the last dose of study drug, and EOT 2 should be performed 2 weeks after last dose of study drug.

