#### 2.1.1 General definitions

##### 2.1.1.1 Study Day 1 and other study days

The first day of administration of randomized study treatment (first dose) is defined as *Study*

*Day 1 or Day 1.*

All other study days will be labeled relative to Day 1. For event dates on or after Day 1, study day for an event date is calculated as Date of event – [Day 1] + 1, i.e., Day 2, Day 3, etc., will be one day, two days, etc., after Day 1, respectively. For event dates before Day 1, study day for an event date is calculated as Date of event – [Day 1], i.e., Day -1, Day -2, etc., will be one day, two days, etc., before Day 1, respectively. Duration of an event will be calculated as (Event end date – Event start date + 1).

The descriptor “Day 0” will not be used.

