## **2.2 Analysis sets**

The following analysis sets will be used for the data analysis. Rules of exclusion criteria of analysis are detailed in [Section 5.6](#).

The **Randomized Analysis Set (RAS)** consists of all randomized subjects. Subjects will be analyzed according to the treatment assigned at randomization.

The **Full Analysis Set (FAS)** comprises all subjects to whom study treatment has been assigned. Subjects will be analyzed according to the treatment assigned to at randomization. Mis-randomized subjects (mis-randomized in IRT) will be excluded from FAS. Mis-randomized subjects are defined as cases where IRT contacts were made by the site either prematurely or

inappropriately prior to confirmation of the subject's final randomization eligibility and no study medication was administered to the subject.

The **Safety Set** includes all subjects who received at least one dose of study treatment. Subjects will be analyzed according to the study treatment received, where treatment received is defined as the randomized/assigned treatment if the subject took at least one dose of that treatment or the first treatment received if the randomized/assigned treatment was never received.

The summary statistics analyses in this study will be performed according to domains with respective specifications of analyses sets, analyses period and treatment groups ([Table 2-1](#)).

**Table 2-1** Summary statistics specifications

Domains	Analyses sets	Analysis Period	Treatment group labels for each analysis period
Patient disposition, Demographics, Other baseline characteristics *	RAS	Treatment Period 1	Secukinumab 300 mg Q4W Placebo Total
		Treatment Period 2 Follow up (only for disposition tables)	Secukinumab 300 mg Q4W Secukinumab 300 mg Q2W Total
Efficacy endpoints	FAS	Treatment Period 1	Secukinumab 300 mg Q4W Placebo
		Entire treatment period	Secukinumab 300 mg Q4W Placebo Placebo-Secukinumab 300 mg Q2W
Safety data (Number of doses, duration of exposure, prior and concomitant therapies, concomitant medical procedures, significant non-drug therapies, laboratory data, AEs, etc.)	Safety set	Treatment Period 1	Secukinumab 300 mg Q4W Placebo
		Entire treatment period	Secukinumab 300 mg Q4W Secukinumab 300 mg Q2W Placebo Any Secukinumab

\* Treatment groups for protocol deviations for entire treatment period: AIN457 300 mg Q4W, AIN457 300 mg Q2W, Any AIN457 300 mg, Placebo, Total

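### The AE start-date rules have no anchor at the Week 16 start of secukinumab, so in placebo-to-Q2W subjects some partially dated events can move from the secukinumab columns to placebo, and none the other way

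*SAP*

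**What the plan says.** SAP 5.1.2 first sets a reference date. An AE that ended before treatment is referred to the earlier of consent and first visit. For every other AE: "Else AE start reference date = treatment start date". The section does not define that term. SAP 2.1.1.1 comes closest: "The first day of administration of randomized study treatment (first dose) is defined as" Day 1.

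The rules that matter for an onset during the study are:

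- Month missing, same calendar year as treatment start (rule 4a): "the imputed AE start date is set to the AE reference start date + 1 day".
- Month missing, later year (rule 3a): 1 January of that year.
- Day missing, same year, month equal to or "greater than the treatment start date month, the imputed AE start date is set to the later of" the first of the month and the reference date plus one day (rule 4c). Rule 3b does the same for a later year.
- Year missing: the start date is left null.
- Imputed start later than the (imputed) end: "then imputed AE start date should be set to the (imputed) AE end date".

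On the switch, SAP 1.1 says "The Week 16 injection is the first injection of Treatment Period 2", and in the placebo arm that injection is the first secukinumab dose. SAP 2.7 analyses safety on actual treatment. For the entire treatment period, Table 2-1 gives separate safety columns for Q4W, Q2W, Placebo and "Any Secukinumab". SAP 2.4.2 says the first secukinumab dose must be considered for visit windows in this arm. Section 5.1.2 has no such provision.

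**The concern.** Subjects who start on placebo contribute to two safety columns, and the onset date is the natural basis for choosing between them. The imputation rules pull an uncertain onset back towards the first study dose. In a trial with one treatment per subject this is cautious, because it makes the event treatment-emergent. In a subject who crosses from placebo to active drug, the same device moves the event off the active drug.

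At stake are the crude incidences for Q2W, Any Secukinumab and Placebo, and the exposure-adjusted rates that Table 2-6 plans for the entire study period. Q2W is the regimen that protocol 4.6 describes as non-approved, and it is observed in no more than 12 subjects per cohort. An error that can only lower its AE count deserves a rule.

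**Working it through.** The documents give no figure on this point to reproduce. The check applies the 5.1.2 rules literally.

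**Inputs.** First study dose = Day 1 (SAP 2.1.1.1). First secukinumab dose in the placebo arm = Week 16, Day 113, which is first dose + 112 days (SAP 1.1 and Table 2-3). Last visit = Week 40, Day 281. Placebo subjects: 12 per cohort, 36 in all (SAP 1.1).

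**Worked cases.**

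| First dose | Switch | True onset | Known part | Imputed start | Column |
|---|---|---|---|---|---|
| 1 March | 21 June | 25 August | year | 2 March | Placebo (wrong) |
| 1 March | 21 June | 25 June | month, year | 1 June | Placebo (wrong) |
| 1 March | 21 June | 25 August | month, year | 1 August | Q2W (right) |
| 1 October | 21 January | March, next year | year | 1 January | Placebo (wrong) |

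**Enumeration.** All 365 first-dose dates of a non-leap year were combined with every post-switch onset day, Day 113 to Day 281 (169 days), equally weighted. Uniform dates are an assumption. This gives 365 × 169 = 61,685 cases.

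*Month missing:*
- Onset in the first-dose year: 28,561 of 28,561 go to placebo (100%).
- Onset in the next year: the rule errs when the switch falls after 1 January, which means a first dose from 12 September on, or 111 dates. 111 × 169 = 18,759 of 33,124 go to placebo (56.6%).
- Together: (28,561 + 18,759) / 61,685 = 47,320 / 61,685 = 76.7%. For a single first-dose date the share ranges from 0% to 100%.

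*Only the day missing:*
- Onset in the switch month: 5,373 of 5,738 go to placebo (93.6%).
- Onset in any later month: 0 of 55,947.
- Together: 5,373 / 61,685 = 8.7%.

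*Reverse error:* over Days 1 to 112 there are 365 × 112 = 40,880 pre-switch cases. None is imputed to the Q2W period under either pattern. The end-date cap can only move a start earlier, so it cannot create a reverse error.

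**Size.** The documents give no rate of partial dates, so the range is assumed.

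| Share of post-switch AEs with this pattern | Moved to placebo, month missing | Moved to placebo, day missing |
|---|---|---|
| 1% | 0.8% | 0.1% |
| 5% | 3.8% | 0.4% |
| 10% | 7.7% | 0.9% |

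One subject is 1/12 = 8.3 percentage points of Q2W crude incidence in a full cohort and 1/36 = 2.8 points pooled. Both are minimum values per subject, because placebo subjects with IGA 0 or 1 at Week 16 do not switch and early dropouts never reach the switch.

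**Cost of the opposite rule.** The rule tested sends a straddling date to the first secukinumab dose unless the end date excludes it. No post-switch event then goes to placebo. Of the 40,880 pre-switch cases, the following are wrongly charged to Q2W:

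| Event ends | Month missing | Day missing |
|---|---|---|
| 7 days after onset | 2,527 (6%) | 2,219 (5%) |
| 14 days after onset | 5,005 (12%) | 3,850 (9%) |
| 30 days after onset | 10,485 (26%) | 5,373 (13%) |
| No end date | 34,552 (84.5%) | 5,373 (13.1%) |

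**The case against.** The strongest reply is that this will hardly ever matter. AEs are sought at every visit, scheduled site visits are at most four weeks apart, and missing values are queried, so a missing month should be rare. A missing day is likelier, but it misplaces events only in the switch month. All of this stands, and it is why the point is minor.

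Two steps are inference. Section 5.1.2 does not define the treatment start date, and the visible SAP does not say how an AE is attributed to the Placebo or the Q2W column. Taking the first from the Day 1 definition and the second from the onset date is the natural reading, but the text does not state either.

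Safety is descriptive, and the randomized comparison is the Treatment Period 1 table. There the same rule can pull month-missing Period 2 events of Q4W subjects back into Period 1, which raises the secukinumab column. A reader might infer that the plan flatters secukinumab throughout. The documents support that direction only for events of placebo-to-Q2W subjects.

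A reader might also infer that all uncertain events in switchers default to placebo. They do not: day-missing events after the switch month are placed correctly, and a missing year gives no date. Nor is it fair to set the 60% of follow-up that lies after the switch, (40 − 16)/40, against the 100% of same-year month-missing events sent to placebo. The first covers the whole follow-up and the second only the first-dose calendar year.

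Finally, a rule favouring the secukinumab period reverses the error and does not remove it. That is right, and large for events with no end date. The choice then rests on which error is safer in a safety table.

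**Conclusion.** The gap is real and minor. Section 5.1.2 has one undefined anchor and no rule for the Week 16 start of secukinumab, although the SAP recognises that dose for visit windows. Where an event of a placebo-to-Q2W subject is misplaced, it moves from Q2W and Any Secukinumab to Placebo, never the reverse. This follows from the rules themselves and does not depend on the uniform-date assumption. The shares of 76.7% (month missing) and 8.7% (day missing) do depend on it.

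A reader might go further and conclude that secukinumab AEs are under-counted. The documents do not show that: it would need partially dated post-switch events, and no rate is given. With at most 36 subjects exposed to the problem, the number is probably very small. It matters mainly because a single subject weighs at least 8.3 points in a cohort's Q2W column.

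**What to change.** In SAP 5.1.2:

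1. Define treatment start date.
2. For placebo-to-Q2W subjects, add a rule for partial dates that straddle the switch. If the known part of the start date allows onset on or after the first secukinumab dose, and the (imputed) end date is not before that dose, set the start to the later of the month start (1 January if the month is missing) and the first secukinumab dose date.
3. List the events this rule touches, and give the AE counts under the opposite assignment.

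The work is a short paragraph, one condition in the date program and one listing. The price is that some true placebo-period events, mainly long or ongoing ones, will be counted under Q2W. That is the conservative direction for safety, and the counts under both assignments show how much depends on it.
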